5. Request for waiver of HIPAA authorization: (When requesting a waiver of HIPAA Authorization for either the entire study, or for recruitment purposes only. Note: if you are collecting PHI as part of a phone or email screen, you must request a HIPAA waiver for recruitment purposes.)

Choose one:

- For entire study
- For recruitment/screening purposes only
- For inclusion of non-English speaking subject if short form is being used and there is no translated HIPAA research authorization form available on the University's HIPAA website at hipaa.yale.edu.

- i. Describe why it would be impracticable to obtain the subject's authorization for use/disclosure of this data: *Write here*
- ii. If requesting a waiver of **signed** authorization, describe why it would be impracticable to obtain the subject's signed authorization for use/disclosure of this data: We request a waiver of signed authorization only for initial participant recruitment/screening purposes to obtain interested participants' phone numbers and/or email for voice and text communication to make initial contact with the research team. At the first phone contact with the research

team, participants will provide verbal consent for the screening process. If participants prefer to complete the online screener through the Yale Qualtrics system, participants will provide signed consent in the online screening.

The investigator assures that the protected health information for which a Waiver of Authorization has been requested will not be reused or disclosed to any person or entity other than those listed in this application, except as required by law, for authorized oversight of this research study, or as specifically approved for use in another study by an IRB.

Researchers are reminded that unauthorized disclosures of PHI to individuals outside of the Yale HIPAA-Covered entity must be accounted for in the “accounting for disclosures log”, by subject name, purpose, date, recipients, and a description of information provided. Logs are to be forwarded to the Deputy HIPAA Privacy Officer.

6. Process of Consent/Accent: Describe the setting and conditions under which consent/assent will be obtained, including parental permission or surrogate permission and the steps taken to ensure subjects' independent decision-making.

After the screening process is complete and the participant is found to be eligible, the RA/PI will schedule them for an in-person (remote if necessary, via phone or video conferencing depending on technological capabilities of participant) intake. At the intake session, all eligible participants will be asked for written consent using the Yale HIC approved combined consent/HIPAA form. If the intake is done remotely, consent will be obtained via Redcap. If the participant has limited internet access, a consent form will be mailed to them. The entire consent form will be reviewed in detail with the participant in a private, one-on-one setting at the first intake appointment. All risks and potential benefits will be described. Any questions the participant may have will be addressed. If the participant wishes, they may consider it further before signing. They may also request to speak to anyone on the research team about questions they have or to consult others, including their physician and family members. Once the participant has signed the consent, they may withdraw consent at any time. Informed consent must be obtained prior to performance of any protocol specific procedures. All participants will receive a signed copy of the consent form to retain for their records.

7. Evaluation of Subject(s) Capacity to Provide Informed Consent/Accent: Indicate how the personnel obtaining consent will assess the potential subject's ability and capacity to consent to the research being proposed.

We will not be enrolling participants with limited decision-making capacity. We plan to exclude individuals with current serious psychiatric or medical illnesses. During the consenting process, the research assistant will read and review the consent form with the prospective participant. The research assistant will then ask the potential participant various questions about the consent form and study protocol to ensure the prospective participant sufficiently understands the study and the nature of their consent to participate.

8. Non-English-Speaking Subjects: Explain provisions in place to ensure comprehension for research involving non-English speaking subjects. If enrollment of these subjects is anticipated, translated copies of all consent materials must be submitted for approval prior to use.

N/A

As a limited alternative to the above requirement, will you use the short form* for consenting process if you unexpectedly encounter a non-English speaking individual interested in study participation and the translation of the long form is not possible prior to intended enrollment? YES NO

Note* If more than 2 study participants are enrolled using a short form translated into the same language, then the full consent form should be translated into that language for use the next time a subject speaking that language is to be enrolled.

Several translated short form templates are available on the HRPP website (yale.edu/hrpp) and translated HIPAA Research Authorization Forms are available on the HIPAA website (hipaa.yale.edu). If the translation of the short form is not available on our website, then the translated short form needs to be submitted to the IRB office for approval via modification prior to enrolling the subject. ***Please review the guidance and presentation on use of the short form available on the HRPP website.***

If using a short form without a translated HIPAA Research Authorization Form, please request a HIPAA waiver in the section above.

9. Consent Waiver: In certain circumstances, the HIC may grant a waiver of signed consent, or a full waiver of consent, depending on the study. If you will request either a waiver of consent, or a waiver of signed consent for this study, complete the appropriate section below.

Not Requesting any consent waivers

Requesting a waiver of signed consent:

- Recruitment/Screening only** (*if for recruitment, the questions in the box below will apply to recruitment activities only*)
- Entire Study** (Note that an information sheet may be required.)

For a waiver of signed consent, address the following:

- Would the signed consent form be the only record linking the subject and the research? YES NO
- Does a breach of confidentiality constitute the principal risk to subjects? YES NO

OR

- Does the research pose greater than minimal risk? YES NO
- Does the research include any activities that would require signed consent in a non-research context? YES NO
 - Why would the research be impracticable to conduct without the waiver? We request a waiver of signed authorization only for initial participant recruitment/screening purposes to obtain interested participants' phone numbers and/or email for voice and text communication to make initial contact with the research team.
 - Where appropriate, how will pertinent information be returned to, or shared with subjects at a later date? At the first phone contact with the research team, participants will provide verbal consent for the screening process. Participants who meet initial eligibility during the screening process will be invited for an in-person meeting to learn more about the study, ask any questions, and provide written informed consent before beginning research activities.

Requesting a waiver of consent:

- Recruitment/Screening only** (*if for recruitment, the questions in the box below will apply to recruitment activities only*)
- Entire Study**

For a full waiver of consent, please address all of the following:

- Does the research pose greater than minimal risk to subjects?
 Yes *If you answered yes, stop. A waiver cannot be granted.*
 No
- Will the waiver adversely affect subjects' rights and welfare? YES NO

SECTION IV: PROTECTION OF RESEARCH SUBJECTS

Confidentiality & Security of Data:

1. What protected health information (medical information along with the HIPAA identifiers) about subjects will be collected and used for the research? We will collect names and demographic information. Identifiable information will be collected and used to enroll and contact participants. It will only be used for this purpose. This information will be stored in locked cabinet apart from the research records.
2. How will the research data be collected, recorded and stored? Research data will be collected using in-person interviews, assessments, objective measures of smoking behavior, and self-reports. All identifiable information (names and demographic information) will be stored in a locked file cabinet. All participants will be assigned a study participant ID made up of numbers and letters. Subsequently, participants will be identified in the Case Report Forms (CRFs) only by that number (e.g., CM24). A list of IDs and the corresponding names will be maintained by the Principal Investigator and stored in a locked research cabinet. All other research data (interviews, assessments, objective measures of smoking behavior, and self-reports) will not contain identifiable information and will be labeled only with the subjects' unique numerical indicator. Patient health information obtained by this study is confidential and may only be disclosed to third parties as permitted by the Compound Consent and Authorization form signed by the patient or unless permitted or required by law.
3. How will the digital data be stored? CD DVD Flash Drive Portable Hard Drive Secured Server Laptop Computer Desktop Computer Other
 Digital data with PHI will be stored on a secured server. Digital data without PHI may be stored and analyzed on a laptop or desktop computer.
4. What methods and procedures will be used to safeguard the confidentiality and security of the identifiable study data and the storage media indicated above during and after the subject's participation in the study? Several steps will be taken to safeguard the confidentiality of subjects and their data. Right to privacy for participation in this research will be protected through coding of data and proper storage of research records. All research data that is collected will be assigned a study participant number and that number will be the only link between participant names/identifying information and the digital databases. The names of participants will not be associated with this data and assessments will be maintained according to participant study number. A master list connecting participant study numbers to participant names will be kept in a locked file cabinet where it can only be accessed by senior level project staff. Any information published as a result of the study will be in aggregate and such that it will not permit identification of any participant. We are not directly assessing incidents of child abuse or elderly abuse. However, if this information is disclosed by a participant or volunteer in the context of this research, a report will be made to the Department of Child and Families Services or other agency as required by law. Subjects will be informed of this limit to confidentiality as it is stated in the informed consent document. All investigators and key personnel have taken the required Yale University HIPAA training. Right to privacy for participation in this research will be protected through coding of data and proper storage

of research records. A list of numbers and the corresponding names will be maintained by the Principal Investigator in a locked research cabinet. Individually identifiable health information will be protected in accordance with the Health Insurance Portability and Accountability Act of 1996 and by additional protections of substance abuse treatment records afforded under Code of Federal Regulations (CFR) Part 2, Subpart E. All research personnel will be trained on human subjects' protection and HIPAA procedures.

All portable devices must contain encryption software, per University Policy 5100. If there is a technical reason a device cannot be encrypted please submit an exception request to the Information Security, Policy and Compliance Office by clicking on url <http://its.yale.edu/egrc> or email [contact]

5. What will be done with the data when the research is completed? Are there plans to destroy the identifiable data? If yes, describe how, by whom and when identifiers will be destroyed. If no, describe how the data and/or identifiers will be secured. The data will be stored in a locked room for 7 years after the final data is collected. After this point, the Data Manager and Principal Investigator will oversee the process in which data is destroyed or de-identified.
6. If appropriate, has a Certificate of Confidentiality been obtained? A certificate will automatically be applied with the federal funding.

SECTION V: POTENTIAL BENEFITS

Potential Benefits: Identify any benefits that may be reasonably expected to result from the research, either to the subject(s) or to society at large. (Payment of subjects is not considered a benefit in this context of the risk benefit assessment.)

The proposed project will provide the FDA with important data regarding the influence of flavors on the abuse potential of e-cigs in adults. The e-cig provides the user with the opportunity to manipulate nicotine content and flavors, which might be attractive to young adult smokers. Thus, it is imperative that we fully understand what young smokers find appealing about this product because such a product has the ability to become widely used. The use of e-cigs is increasing and could become a future epidemic among young users with potentially harmful health consequences. Developing an understanding of how sweet and cool flavors influence appeal among young adults who are susceptible to future e-cigarette use is crucial to the regulation of the constituents of existing and future modified risk tobacco products. Additionally, addressing whether sweet, cool and tobacco flavors differentially alter nicotine reward and use of e-cigs among younger and older adult combustible tobacco users who might be trying to switch to e-cigarettes for harm-reduction is important. Older combustible tobacco users may not need flavors to increase the palatability of tobacco products and to benefit from switching to e-cigs. The goals of this project are to develop a comprehensive understanding of flavors and other tobacco constituents on nicotine's addictive potential and the appeal and use of tobacco products.

SECTION VI: RESEARCH ALTERNATIVES AND ECONOMIC CONSIDERATIONS

1. **Alternatives:** What other alternatives are available to the study subjects outside of the research?
Write here
2. **Payments for Participation (Economic Considerations):** Describe any payments that will be made to subjects, the amount and schedule of payments, and the conditions for receiving this compensation.
As an economic consideration, we will compensate participants for time spent in this research project.

Participants in Study 1 (n=40) will receive \$50 for the intake, \$100 for the Lab visit, and \$25 cash/Amazon gift card for the the follow up visits (1 month). Participants can be compensated up to \$20/in person visit for travel (up to \$40). Thus, each participant can earn up to \$215 for Study 1.

Participants may earn a \$25 referral bonus for each friend that is referred to participate in this study. In order to receive this bonus, the friend(s) must complete the intake appointment and physical exam.

Participants in Study 2 will receive \$50 for Intake and \$25 for in-person intake. If ineligible after intake, participants will receive compensation in the form of an electronic gift card of their choosing (examples include but are not limited to Amazon, Wal-Mart, Target, Stop & Shop). If they do not have an email account, a gift card will be mailed to them. Participants in Study 2 (n=120) will receive escalating payments per lab session to increase completion (\$50 for Lab 1, \$75 for Lab 2, \$100 for Lab 3, \$125 for Lab 4) and a \$25 gift card for each of the follow up visits (1 month, 6 month).

Both studies will compensate participants \$20/day for travel to appointments after the initial intake (up to \$100, follow ups will conducted over the phone). Thus, each participant in Study 1 can earn a total of \$215 (including value of gift cards) and each participant in Study 2 can earn up to \$575 (including value of gift cards). If participants have borrowed a study cell phone from us for the study, we will ask that they return the cell phone at the last visit. The final visit payment will be withheld until the cell phone is returned. Participants enrolled in the study will be paid via cash or in some cases (see above) gift cards. As the ad-lib portion of Study 2 is on hold, participants will not receive payments associated with the ad-lib portion of the study (i.e. compensation for daily CosCOs, questionnaires, ad-lib visits, as well as returning the e-cigarette and battery).

Participants may earn a \$25 referral bonus for each friend that is referred to participate in this study. In order to receive this bonus, the friend(s) must complete the intake appointment and physical exam.

We will validate parking in the Air Rights parking garage. We will provide round trip cab transportation to appointments after the remote intake, if transportation is an issue.

3. **Costs for Participation (Economic Considerations):** Clearly describe the subject's costs associated with participation in the research, and the interventions or procedures of the study that will be provided at no cost to subjects.
There are no costs for participation.
4. **In Case of Injury:** This section is required for any research involving more than minimal risk, and for minimal risk research that presents the potential for physical harm (e.g., research involving blood draws).
 - a. Will medical treatment be available if research-related injury occurs? *Write here*
 - b. Where and from whom may treatment be obtained? *Write here*
 - c. Are there any limits to the treatment being provided? *Write here*
 - d. Who will pay for this treatment? *Write here*
 - e. How will the medical treatment be accessed by subjects? *Write here*

(a-e) If a participant is injured as a direct result of participation in this study, treatment will be provided. The participant and/or his or her insurance carrier will be expected to pay the costs of this treatment. No additional financial compensation for injury or lost wages is available. Participants will not waive their legal rights by participating in this study.

IMPORTANT REMINDERS

Will this study have a billable service? **Yes** **No**

A billable service is defined as any service rendered to a study subject that, if he/she was not on a study, would normally generate a bill from either Yale-New Haven Hospital or Yale Medical Group to the patient or the patient's insurer. The service may or may not be performed by the research staff on your study, but may be provided by professionals within either Yale-New Haven Hospital or Yale Medical Group (examples include x-rays, MRIs, CT scans, specimens sent to central labs, or specimens sent to pathology). Notes: 1. There is no distinction made whether the service is paid for by the subject or their insurance (Standard of Care) or by the study's funding mechanism (Research Sponsored). 2. This generally includes new services or orders placed in EPIC for research subjects.

If answered, "yes", this study will need to be set up in OnCore, Yale's clinical research management system, for Epic to appropriately route research related charges. Please contact [contact]

Are there any procedures involved in this protocol that will be performed at YNHH or one of its affiliated entities? **Yes** **No**

If Yes, please answer questions a through c and note instructions below.

- a. Does your YNHH privilege delineation currently include the **specific procedure** that you will perform? **Yes** **No**
- b. Will you be using any new equipment or equipment that you have not used in the past for this procedure? **Yes** **No**
- c. Will a novel approach using existing equipment be applied? **Yes** **No**

If you answered "no" to question 4a, or "yes" to question 4b or c, please contact the YNHH Department of Physician Services ([name]) for prior approval before commencing with your research protocol.

IMPORTANT REMINDER ABOUT RESEARCH AT YNHH

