Study 2 will use established experimental methods to examine if different classes of flavors (i.e., sweet, cool, tobacco), when combined with nicotine concentrations differing in harshness (6 and 18 mg/ml) alter appeal and nicotine reward among younger and older combustible tobacco users. Importantly, this study will also explore the differential influence of sweet, cool, and tobacco flavors on switching from combustible tobacco product use to e-cigarettes, among younger and older adult combustible tobacco users. The evidence generated from this novel proposal is crucial to support regulations directed at flavors in tobacco/nicotine products like e-cigs, which will likely need to strike a balance between reducing the appeal of these products for youth and enhancing their appeal for combustible tobacco users looking to switch to use of e-cigs for harm-reduction.

4. **Research Plan:** Summarize the study design and research procedures using non-technical language that can be readily understood by someone outside the discipline. **Be sure to distinguish between standard of care vs. research procedures when applicable and include any flowcharts of visits specifying their individual times and lengths.** Describe the setting in which the research will take place.

We propose 2 double-blind, placebo-controlled studies.

Study 1B: Examine the influence of sweet and cooling flavors on the appeal and abuse potential of nicotine-containing e-cigs among susceptible young adults. Forty young adults (18-20 years of age) who have used e-cig use (used at least 10x in lifetime and at least once in the past 30-days), will participate in 1 laboratory session, and receive all the exposures in table below.

Sweet (Watermelon)		
	Non-menthol	Menthol
36 mg/ml nicotine salt	S ₁ -S ₄₀	S ₁ -S ₄₀

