All participants will have an extensive medical history evaluation reviewed by the study APRN and be deemed healthy prior to participation and will continue to monitor their health closely during the study. Participants will be informed that if they experience any symptoms (cough, shortness of breath, chest pain, nausea, vomiting, stomach pain, diarrhea, fever, chills, or weight loss) or have other concerns, that they should let us know and also let their doctor know right away. Any participants reporting mild or moderate respiratory symptoms will be referred to their primary care physician. They will be informed to the emergency room right away if their symptoms are severe increase rapidly. It is possible that the hospital may report cases of illness after using e-cigarettes to the State Health Department and the CDC. The report will contain the name and address of the person who is ill. Given the risk of THC vaping and EVALI, participants who report THC vaping and have endorsement of these symptoms at baseline without reasonable and proximal cause will be ineligible. If these participants develop symptoms during the study without reasonable and proximal cause, they will be withdrawn.

The lab sessions will be conducted by trained research staff who are sensitive to the smoking population and trained to monitor any potential adverse effects. Heart rate, blood pressure, and pulse oximetry will be assessed at baseline and every in-person visit for safety. If they experience any side effects or concerns during the study, we ask them to let us know. Participants will be told that they are able to stop the study at any point. If they feel any discomfort or need to stop for any reason, they can let the research team know. We will also provide participants with referral sources to quit smoking if they are interested.

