4. **Storage, Preparation and Use:** Describe the method of storage, preparation, stability information, and for parenteral products, method of sterilization and method of testing sterility and pyrogenicity. After the e-liquids are received, they will be delivered and stored in appropriate light/temperature conditions at John Pierce Labs, which is a secured building. The liquids will be kept in a locked storage container in a drawer within the lab room. On the day prior to the lab sessions, a research assistant/associate/fellow who is not involved in the actual conduct of the lab sessions will fill the e-cigs. The information on randomizations to nicotine condition and flavors for each lab session has been generated by study biostatisticians. This information is stored for each participant in an individual envelope and a printed study ID on the cover. These envelopes are stored at Pierce lab along with the purchased e-liquids. The individual filling the pods will be notified of which subject ID number needs to be filled and they will then go to Pierce labs and open the envelope and fill the three pods with the appropriate e-liquids. First, they will label each pod with the study ID number and lab 1, 2 and 3 respectively. Each bottle of e-juice will be shaken vigorously prior to filling the pods. Next, they will open the top of the pod and using a mechanical pipette will load .9ml into the pipette from the e-juice bottle and carefully transfer it into the pod. This will be completed for all lab sessions in both studies. Each pod is then stored in a separate airtight bag to avoid cross contamination of flavors. The individual bags are then stored together in a larger bag labeled with the study ID number and stored back in the locked container until the lab is set to begin. Once the research assistant is ready to begin each lab, they will open the locked container, take the appropriate pod and leave the others. At the end of the lab, they will return the pod used that day to its proper bag and again return it to the lock box. The research staff will have the group randomization list and will dispense the appropriate e-liquid (nicotine level, flavor) needed for each subject.

Check applicable Investigational Drug Service utilized:

YNHH IDS

CMHC

Pharmacy

West Haven VA

PET Center None
 Other: John Pierce Lab, WCRU (West Campus Research Unit)

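### The protocol calls both studies double-blind, but the last sentence on pod handling gives research staff the randomization list and, read as written, unblinds the people who run the sessions

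*Combined protocol and SAP*

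**What the plan says.** Section I.4 (Research Plan) states: "We propose 2 double-blind, placebo-controlled studies".

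Section II, Drugs/Biologics, item 4 (Storage, Preparation and Use) describes how the allocation is handled. The biostatisticians generate it. "This information is stored for each participant in an individual envelope and a printed study ID on the cover". On the day before a session, "a research assistant/associate/fellow who is not involved in the actual conduct of the lab sessions will fill the e-cigs". That person opens the envelope and prepares the pods: "First, they will label each pod with the study ID number and lab 1, 2 and 3 respectively". On the session day the research assistant goes to the store; "they will open the locked container, take the appropriate pod and leave the others". The used pod goes back the same way.

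The item then closes with: "The research staff will have the group randomization list and will dispense the appropriate e-liquid (nicotine level, flavor) needed for each subject".

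Section I.10 (Risks) says who the research staff are in the rest of the protocol: "The lab sessions will be conducted by trained research staff". The same section also has research staff monitoring e-cigarette use during the session.

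**The concern.** Up to its final sentence, item 4 keeps session staff blind. They handle a pod that carries a code and need to know nothing else. The final sentence gives research staff the group list and has them dispense by nicotine level and flavor. If these are the people who run the sessions, the studies are blind for participants at most. Participants may well recognize a flavor by taste, so the blind matters most for nicotine level and for how staff behave toward the participant.

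The outcomes are of a kind that expectation can move. Study 1 liking is a self-rating on the Labeled Hedonic Scale, the sensory ratings use the gLMS, and Study 2 liking/wanting is a 0 to 100 mm self-rating on the adapted Drug Effects Questionnaire. Salivary nicotine and cotinine are reserved for correlational analyses, so no objective primary outcome stands behind the ratings.

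**Working it through.** **1. Who is meant by research staff.** Three points suggest session staff. Section I.10 uses the term for those who conduct and monitor sessions. The sentence follows directly on the session-day steps. The filler is described separately and works from individual envelopes, not from a group list. Three points suggest the filler. The filler is also a research assistant, associate or fellow. Item 2 of the same part says the solutions are dispensed at the laboratory where they are stored and the pods filled. What is dispensed in the sentence is e-liquid, and on the session day the pod is already full. The text does not settle the question.

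**2. Whether session staff need the list.** They take a filled pod identified by study ID and lab number, run the session and return the pod. No step described requires the allocation, and the protocol gives no reason for session staff to hold it.

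**3. Which comparisons are exposed.**
- *Study 2, nicotine level.* Section I.1 expects cool flavors to alter liking/wanting at 18 mg/ml but not at 6 mg/ml. Nicotine level is a randomized between-subject factor, and the list reveals both level and flavor. This is the main exposure.
- *Study 2, primary contrast in Section I.13.* This compares age groups on flavor preference within 18 mg/ml. Everyone in it has the same concentration, so knowledge of the concentration alone does not separate the groups. Bias requires staff influence that differs by age group or by flavor.
- *Study 1.* Both exposures are at 36 mg/ml. The list can reveal only which exposure is the menthol one.

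**4. Illustration of size.** No figure in the plan depends on this point. The group sizes are the plan's own: 120 × 0.9 = 108 completers in Study 2, hence 54 per concentration and 27 per age group within a concentration; and 40 × 0.9 = 36 in Study 1. As a check on those sizes, the stated 82% power for Study 2 reproduces with a one-degree-of-freedom contrast among the 54 at 18 mg/ml: noncentrality 54 × 0.4² = 8.64 on F(1, 52) gives 82.2%.

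Assume there is no true effect and staff expectation shifts the compared score by b standard deviations. Here SD means the SD of the per-participant score being compared, or of the paired difference in Study 1. The rejection rate of a two-sided 5% t test then comes from a noncentral t distribution with noncentrality b√(n/2) for two groups of n, or b√n for n pairs.

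| Comparison | df | Noncentrality at b = 0.1 / 0.2 / 0.3 | False-positive rate |
|---|---|---|---|
| 6 v 18 mg/ml, 54 v 54 | 106 | 0.52 / 1.04 / 1.56 | 8.1% / 17.8% / 33.9% |
| Age groups within 18 mg/ml, 27 v 27 | 52 | 0.37 / 0.73 / 1.10 | 6.5% / 11.1% / 19.1% |
| Study 1 menthol v non-menthol, 36 pairs | 35 | 0.60 / 1.20 / 1.80 | 9.0% / 21.5% / 41.7% |

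The values of b are assumptions; nothing in the documents supports a particular one. The second row applies only if the shift differs between the age groups. A shift by nicotine level that is the same for every flavor would cancel from the dose-by-flavor comparison, so bias there also needs the shift to vary by flavor.

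**The case against.** The strongest reply is that the sentence loosely restates the filler's job and that practice is blinded already. That is possible, for the reasons in step 1, and the lack of any use for the list in a session fits it. It does not dispose of the point: even on that reading the sentence excludes nobody from the list, and the general term it uses elsewhere covers those who run sessions.

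A second reply is that staff have limited means of influencing the ratings. This stands in part. The gLMS and the hedonic scale are shown on screen, with mouse entry stated for the gLMS; Section I.13 has outcomes collected on scannable forms; and Section I.4 provides recorded, timed puffing instructions for Study 2. A reader might infer that staff take all the primary ratings face to face, but the documents do not say so. Staff are still present and monitor use, so influence is reduced, not excluded.

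A third reply is that the nicotine-level argument does not reach the planned primary contrast or Study 1. This is largely right. A reader might take the larger false-positive rates as applying to the primary results of both studies. They do not: Study 1 has one concentration, and the Study 2 primary contrast lies within one concentration.

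**Conclusion.** The inconsistency is real. The last sentence of the storage and preparation item conflicts with the double-blind description and with the blind built earlier in the same item. Read as written, it unblinds session staff. That they are unblinded in practice is a stronger conclusion, which the text does not establish.

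The consequence is greatest for the Study 2 hypotheses that involve nicotine level, smaller for the age-by-flavor contrast within 18 mg/ml, and confined to knowledge of menthol versus non-menthol order in Study 1. The size of any bias cannot be derived from the documents, and the tabulated rates only show what an assumed shift would do. The sentence should be corrected because the blind is worth having and almost all of the arrangements for it already exist.

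**What to change.** Replace the last sentence of Section II, Drugs/Biologics, item 4 with text to this effect:

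> Only the study biostatisticians and the pod filler, who conducts no lab sessions, have access to the randomization list and the participant envelopes. The envelopes are kept where session staff cannot open them. Session staff receive pods labelled only with study ID and lab or exposure number, for every session and exposure in both studies.

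Two details need attention in the same edit. The envelopes are now kept alongside the e-liquids, and session assistants open the locked container on session days, so the place of storage should be stated. The labels described run to lab 3, whereas Section I.4 has four sessions in Study 2 and two exposures within one session in Study 1. The coding scheme should be reconciled with both.

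The cost is a short text change, a separate secure place for the envelopes and a longer label series. The filler, envelopes and coded pods are already in the plan, so no extra staff are needed.
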